2.4 Primary Endpoints

2.4.1 Primary Immunogenicity Endpoints

The primary immunogenicity endpoints of this study are:

- **Mucosal seroconversion (nasal mucosal secretion sampling):** Proportion of subjects who achieve seroconversion against at least 1 pertussis antigen (PT, FHA, PRN, FIM 2/3, or BPZE1 whole cell extract) in nasal secretions on Day 29 or 113 (prime or prime + boost).
Mucosal seroconversion is defined as a 2-fold increase over the baseline value (collected during screening) or a 4-fold increase over the minimal limit of assay detection (whenever the baseline value falls below the limits of assay detection) for any of the pertussis-specific antibodies (S-IgA ELISA): PT, FHA, PRN, FIM 2/3, or

BPZE1 whole cell extract. Seroconversion will be calculated based on absolute titer response over baseline **and** by standardizing pertussis-specific ELISA responses relative to non-pertussis-specific total nasal mucosal secretion (eg, IgA). To be further defined during assay development and within the statistical analysis plan.

Mucosal baseline samples will be taken at the screening visit.

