8.1. Primary Immunogenicity Analyses

The primary immunogenicity endpoint of this study is mucosal seroconversion (nasal mucosal secretion sampling) defined as the proportion of subjects who achieve seroconversion against at least 1 pertussis antigen (PT, FHA, PRN, FIM 2/3, or BPZE1 whole cell extract) in nasal secretions on Day 29 for the prime vaccination or Day 113 for the prime + boost vaccination.

Mucosal seroconversion is defined as a 2-fold increase over the baseline value (collected during screening) or a 4-fold increase over the minimal limit of assay detection (whenever the baseline value falls below the limits of assay detection) for any of the pertussis-specific antibodies (S-IgA ELISA): PT, FHA, PRN, FIM 2/3, or BPZE1 whole cell extract.

Seroconversion will be calculated based on absolute titer response (based on IgA) over baseline **and** by standardizing pertussis specific ELISA responses relative to non-pertussis specific total mucosal secretion (Total IgA). Overall mucosal seroconversion defined as either seroconversion based on absolute titer response (based on IgA) or seroconversion based on standardizing pertussis specific ELISA responses relative to non-pertussis specific total mucosal secretion (Total IgA).

Any pertussis antigen specific antibody titer (PT, FHA, PRN, FIM 2/3, or BPZE1 whole cell extract) from nasal mucosal sample that is below the minimal limit of assay detection will be imputed with a value equal to half of the minimal limit of assay detection of the antigen specific antibody titer.

The proportion of subjects who achieved mucosal seroconversion on Day 29/Visit 3 or Day 113/Visit 8 will be summarized based on the Immunogenicity Analysis Set. Baseline is defined as the last non-missing value collected before the prime vaccination.

Data will be summarized using frequency counts and percentages.

A by-subject listing will be provided for mucosal immunogenicity data as collected based on Immunogenicity Analysis Set.

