8.2.2. Secondary Mucosal Immunogenicity Analyses

Secondary mucosal immunogenicity endpoints are as described in Section 3.2.2.2.

Summaries and analyses will be the same as secondary systemic immunogenicity endpoints with the following exceptions:

1. the pre-boost baseline is defined as the value collected on Day 78/Visit 4 prior to boost vaccination. If the visit is missed on Day 78 but the subject arrives for boost vaccination, then a sample obtained prior to the vaccination will be used as the pre-boost value.
2. All mucosal immunogenicity endpoints will be calculated and summarized based on absolute titer response over baseline and by standardizing pertussis specific ELISA responses relative to non-pertussis specific total mucosal secretion of total IgA .

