- Solicited local, nasal/respiratory, subjective systemic reactogenicity on each day (Appendix 13.1) by toxicity grade based on FDA standard (Table 9-1).
- Overview of TEAE, TEAE by SOC/PT, TEAE by severity grade, SAE, and SAE related to study vaccination.
- Change from baseline of laboratory test (hematology and serum chemistry) and vital sign tests on Day 2 (Visit 2)
- Summary of laboratory and vital sign tests by toxicity grade on Day 8 (Visit 2) (Appendix 13.2, 13.3)
- By-subject listing will also be provided to support the above tables. In addition, a by-subject listing of IP administration will also be provided.

11. Changes in the Planned Analysis

The SAP contains no changes in the planned analyses described in the protocol.

12. References

Department of Health and Human Services (DHHS), Food and Drug Administration, Center for Biologics Evaluation and Research (US). Guidance for industry: Toxicity grading for healthy adult and adolescent volunteers enrolled in preventive vaccine clinical trials. September 2007 [cited 2017 Nov 29]. Available from: <https://www.gpo.gov/fdsys/pkg/FR-2007-09-27/pdf/E7-19155.pdf>

ILiAD Biotechnologies. BPZE1. Investigator's brochure, 0.42 ed. Weston (FL); 2017. 44 p.

13. Appendices

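### SAP 8.1 names no primary scale for mucosal seroconversion and adds an either-scale 'Overall' responder that inflates the descriptive primary rate; it also leaves the detection-limit rule undefined for ratios

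*SAP*

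**What the plan says.** SAP 8.1 gives this primary immunogenicity endpoint: "proportion of subjects who achieve seroconversion against at least 1 pertussis antigen (PT, FHA, PRN, FIM 2/3, or BPZE1 whole cell extract"). It is measured on nasal samples, at Day 29 after the prime or Day 113 after prime plus boost. The threshold is: "Mucosal seroconversion is defined as a 2-fold increase over the baseline value (collected during screening) or a 4-fold increase over the minimal limit". The second limb applies to subjects whose baseline is undetectable.

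Protocol 2.4.1 and 7.1 have this calculated on the absolute titre and also "by standardizing pertussis-specific ELISA responses relative to non-pertussis-specific total nasal mucosal secretion (eg, IgA"), with the note "To be further defined during assay development and within the statistical analysis plan". SAP 3.2.1.1 repeats both calculations. SAP 8.1 repeats them and then adds "Overall mucosal seroconversion defined as either seroconversion based on absolute titer response (based on IgA) or seroconversion based on standardizing" to total IgA. This is the only rule given for combining the scales.

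SAP 8.1 does not say whether the primary proportion is the absolute, the standardised or the overall version. A specific titre below the limit "will be imputed with a value equal to half of the minimal limit of assay detection of the antigen specific antibody titer"; how the limit works on the ratio scale is not stated. The only sensitivity analysis of the primary endpoint (SAP 8.3) changes the analysis set, not the scoring.

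SAP 8.2.2 adds: "All mucosal immunogenicity endpoints will be calculated and summarized based on absolute titer response over baseline and by standardizing pertussis specific ELISA responses". SAP Section 11 states: "The SAP contains no changes in the planned analyses described in the protocol".

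**The concern.** The usual reason to divide by total IgA is that the amount of secretion recovered varies between samples. If recovery doubles, specific and total IgA both double: the ratio is unchanged, but the absolute titre has risen 2-fold. An either-scale rule accepts that sample, so it gives back what standardising took out. It also lets in the opposite error: if total IgA falls while specific IgA is flat, the ratio rises and the standardised limb is met.

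No formal hypothesis is tested, so the estimated proportion is itself the study's primary immunogenicity result, and Protocol 3.1.1 says an adequate immune response must be shown to advance to later trials. A rate with a large chance component is hard to interpret. A reader who is not told which of three versions is primary cannot tell which one was intended before the data were seen.

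**Working it through.** **Plan's own figure.** SAP Table 4-1 gives 63.1 to 76.3% (width 13.1) for a 70% response at N = 200. Clopper-Pearson with x = 140, n = 200: lower = Beta(0.025; 140, 61) = 63.1%, upper = Beta(0.975; 141, 60) = 76.3%. All 20 cells reproduce to within 0.05 points. The table is right, but its intervals describe sampling error around whatever rate the scoring rule produces.

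**Direction.** With A = absolute responder and S = standardised responder, P(A or S) = P(A) + P(S) − P(A and S), which is at least the larger of P(A) and P(S). This needs no assumption.

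**Size (assumed inputs).** The documents give no assay or sampling variability, and SAP 8.2.1 leaves the detection limits to be set after assay validation. Take independent normal errors on the log2 scale with per-sample SDs r (recovery, shared by all antigens), a (each antigen) and t (total IgA). A change is a difference of two samples, so each SD is multiplied by √2. Baselines are above the limit.

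- Absolute change for antigen j = R + A_j
- Standardised change for antigen j = A_j − T (recovery cancels)
- Event if the change is at least 1 (2-fold) for any of 5 antigens

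Chance seroconversion with no true change, 400,000 simulated subjects per row:

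| r / a / t (log2 SD) | Absolute | Standardised | Either | Both |
|---|---|---|---|---|
| 0.5 / 0.3 / 0.3 | 25.1% | 16.0% | 35.2% | 5.9% |
| 0.7 / 0.35 / 0.35 | 34.1% | 23.6% | 47.5% | 10.2% |
| 1.0 / 0.4 / 0.6 | 40.8% | 35.4% | 60.2% | 16.0% |

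Check on row 1: 25.1 + 16.0 − 5.9 = 35.2. The union exceeds the larger component by 10.1, 13.4 and 19.4 points.

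The same model with SDs set from coefficients of variation, log2 SD = √ln(1 + CV²) / ln 2:

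| Sampling CV / assay CV | Absolute | Standardised | Either |
|---|---|---|---|
| 50% / 10% | 21.7% | 0.1% | 21.8% |
| 50% / 20% | 29.9% | 13.9% | 38.3% |
| 75% / 30% | 41.4% | 33.5% | 58.7% |
| 0% / 20%, total-IgA CV 50% | 3.3% | 29.8% | 31.3% |

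In the first row the union is practically the absolute rate, so standardising achieves nothing. In the last row standardising is the source of the error. The union takes on whichever scale is noisier.

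**Share due to five antigens.** At 50% / 20%, one antigen alone gives 17.0% absolute, 4.0% standardised and 19.6% either. Formula check: the CVs give log2 SDs of 0.682 and 0.286. The absolute change has SD √2 × √(0.682² + 0.286²) = 1.05, and 1 − Φ(1/1.05) = 17%. With any of five the union is 38.3%, so much of the base rate comes from the protocol's rule.

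**Contrast between groups.** At 50% / 20%, a group with a true 2-fold rise in all antigens scores 68.1 / 83.4 / 93.5% (absolute / standardised / either). Subtracting the null rates gives 68.1 − 29.9 = 38.2, 83.4 − 13.9 = 69.5 and 93.5 − 38.3 = 55.2 points. The union loses 14.3 points against the cleaner scale, though here it still beats the absolute scale.

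**Detection limit L; T0 and T1 = total IgA at baseline and post-dose.**

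- Baseline exactly L, post-dose undetectable (imputed 0.5 L). The baseline is not below L, so the 2-fold limb applies. Ratio = (0.5 L/T1) / (L/T0) = 0.5 × T0/T1, which is at least 2 when T0/T1 is at least 4. A 4-fold fall in total IgA makes a responder of a subject with no detectable antibody. The chance is 1 − Φ(2/SD): about 0%, 2.3% and 9.1% for an assumed log2 SD of the change in total IgA of 0.5, 1.0 and 1.5.
- Undetectable at both visits. Three readings are open. (i) The 4 × L limb on raw titre: 0.5 L never reaches 4 L, so 0%. (ii) The limb carried to ratios: 0.5 L/T1 ≥ 4 L/T0 needs an 8-fold fall, 1 − Φ(3/SD) = about 0%, 0.1% and 2.3%. (iii) The 2-fold rule on the imputed ratio T0/T1: 1 − Φ(1/SD) = 2%, 16% and 25%.

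**The case against.** Several points on the other side stand.

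- A reader might infer that the union is the headline rate. SAP 8.1 does not say so: its summary sentence refers to mucosal seroconversion without the word overall.
- The union hides nothing. SAP 8.2.2 requires mucosal endpoints on both scales, and SAP 3.2.2.2 includes at least one antigen on each sampling day, which covers Days 29 and 113.
- A reader might take Section 11 as concealing a protocol change. The protocol expressly left the definition to the SAP, so this is not plainly an undeclared change.
- A reader might conclude that the standardised scale is the right one. No passage shows that, and the last CV row above gives 29.8% standardised against 3.3% absolute.
- The 2%, 16% and 25% figures for subjects undetectable at both visits hold only on reading (iii). The SAP has a separate limb for baselines below the limit, so the worst reading cannot be stated as fact.
- Day 29 is not without any near-null group. Arms C and D receive nasal placebo with Boostrix, and Protocol 3.1.1 does not expect a measurable whole-cell response from the acellular vaccine. That helps for one antigen, not for any of five.
- The rule applies to every arm, so it need not favour BPZE1.

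These points limit the severity. They do not remove the missing primary scale, the permissive composite in the primary section, or the gap in the detection-limit rule.

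**Conclusion.** The point holds as a should-fix. SAP 8.1 leaves the primary proportion ambiguous among three versions, and its only composite is the most permissive. That the union is at least as high as either component is certain. The size is conditional: about 35-60% chance seroconversion, against 25-41% absolute and 16-35% standardised, rests on assumed log2 SDs of 0.5-1.0 (recovery), 0.3-0.4 (antigen) and 0.3-0.6 (total IgA), and includes the protocol's any-of-five effect. Contrasts between arms can shrink relative to the cleaner scale (69.5 to 55.2 points in the case worked), but not necessarily relative to the noisier one.

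Separately, if the 2-fold rule is applied to ratios as written, a subject with baseline at the limit and undetectable post-dose antibody can count as seroconverted. For baselines below the limit the SAP is silent on ratios.

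A reader might call this type I error inflation or a bias towards BPZE1. Neither follows: SAP Section 4 tests no hypothesis, and the rule is common to all arms. The harm is to a descriptive primary rate and to knowing which rate it is.

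**What to change.** Amend SAP 8.1 before unblinding:

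- (a) Do not use the either-scale composite as the primary proportion. Name one scale as primary and report the other beside it. Standardised is the natural choice if the precision of the total-IgA assay supports it. If the union is kept, show it as supportive only, with the absolute-by-standardised cross-table for each arm.
- (b) On either scale, count seroconversion only if the raw post-dose titre is detectable, and at least 4 times the detection limit when the baseline is below that limit.
- (c) Add an any-of-five roll-up of the 2-fold rise from Day 78 to Day 113 in Arms D and B, who receive nasal placebo on Day 85, as an internal estimate of the chance rate. The per-antigen version is already planned (SAP 3.2.2.2). Read it as approximate, because a waning response to the prime, especially in Arm B, would lower it.

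Noting the composite in Section 11 is optional, since the protocol delegated the definition. The cost is SAP wording and one table from data already collected; no samples or visits are added. The downside is a lower reported proportion.

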8.2. Secondary Immunogenicity Analyses

8.2.1 Secondary Systemic Immunogenicity Analyses

All secondary systemic immunogenicity endpoints are as described in section 3.2.2.1.

Systemic seroconversion is defined as a 2-fold increase over the baseline value or a 4-fold increase over the minimal limit of assay detection (whenever the baseline value falls below the limits of assay detections).

Seroconversion, GMT and GMFR will be derived using titer results based on IgA, IgG and IgA or IgG for all the acellular pertussis antigens (PT, FHA, PRN, FIM2/3). For BPZE1 whole cell extract, titer results based on IgG will be used to derived seroconversion, GMT and GMFR.

The secondary systemic immunogenicity endpoints are:

8.2.1.1. Proportion of subjects who achieve seroconversion against pertussis antigen (PT, FHA, PRN, FIM 2/3, or BPZE1 whole cell extract) over (pre-prime) baseline based on Immunogenicity Analysis Set for the following:

- At least 1 antigen **on each** of the Days 29, 85, 113, 169, or 254
- At least 1 antigen **on any** of the Days 29, 85, 113, 169, or 254
- At least **any 1** antigen **on all** Days 29, 85, 113, 169, and 254

8.2.1.2. Proportion of subjects who achieve seroconversion (IgG ELISA only) against BPZE1 whole cell extract over (pre-prime) baseline based on Immunogenicity Analysis Set for the following:

- On **either** Day 29 (prime) or 113 (boost)
- On **both** Days 29 (prime) and 113 (boost).

8.2.1.3. Proportion of subjects who achieve seroconversion against all acellular pertussis antigens PT, FHA, and PRN over (pre-prime) baseline based on Immunogenicity Analysis Set for the following:

- On **either** Day 29 (prime) or 113 (boost)
- On **both** Days 29 (prime) or 113 (boost).

8.2.1.4. Proportion of subjects who achieve seroconversion against 2 or more pertussis antigens (PT, FHA, PRN, FIM 2/3, and BPZE1 whole cell extract) over (pre-prime) baseline based on Immunogenicity Analysis Set for the following:

- On **each** of the Days 29, 85, 113, 169, or 254
- On **any** of the Days 29, 85, 113, 169, or 254
- At least the same **2 antigens** on **all** Days 29, 85, 113, 169, and 254.

8.2.1.5. Proportion of subjects who demonstrate boosting for each pertussis antigen (PT, FHA, PRN, FIM 2/3, and BPZE1 whole cell extract) on Day 113 based on Immunogenicity Analysis Set. Boost is defined as at least a 2-fold increase from the pre-boost baseline.

8.2.1.6. The Geometric Mean Fold rise (GMFR) against each pertussis antigen (PT, FHA, PRN, FIM 2/3, and BPZE1 whole cell extract):

- On Days 29, 85, 113, 169, and 254 **over (pre-prime) baseline** based on Immunogenicity Analysis Set.
- On Days 113, 169, and 254 **over pre-boost** (Day 85) based on Immunogenicity Analysis Set.
- The maximum **over (pre-prime) baseline** on either Day 29 or 85 (post-priming response) based on Immunogenicity Analysis Set.
- The maximum **over pre-boost** (Day 85) on any of the Days 113, 169, or 254 (post-boost response) based on Immunogenicity Analysis Set.
- The maximum **during** the study based on Immunogenicity Analysis Set using (pre-prime) baseline.

8.2.1.7. The Geometric Mean Titer (GMT) against each pertussis antigen (PT, FHA, PRN, FIM 2/3, and BPZE1 whole cell extract):

- On Days 29, 85, 113, 169, and 254 based on Immunogenicity Analysis Set
- The maximum on Day 29 or 85 (after priming dose) based on Immunogenicity Analysis Set.
- The maximum after Days 113, 169, or 254 (after boosting dose) based on Immunogenicity Analysis Set.
- The maximum **during** the study based on Immunogenicity Analysis Set.

For systemic immunogenicity endpoints, unless otherwise specified, baseline will refer to the pre-prime baseline (defined as the last non-missing serum sample taken at Day 1/ Visit 1 prior to prime vaccination) and will be used for summaries based on Immunogenicity Analysis Set, as applicable. Pre-boost baseline is defined as the value collected on either Day 78/Visit 4 or Day 85/Visit 5 prior to boost vaccination and will be used for summaries based on Immunogenicity Analysis Set, as applicable. Data will be summarized based on the endpoint type as described in Section 3.2. Analyses will include the GMTs along with corresponding 95% CIs and GMFR at each time point and maximum titer or ratio at any time point.

For all systemic immunogenicity endpoints, summaries against each of the following Pertussis antigen specific antibodies will be provided based on results from IgA and IgG (PT, FHA, PRN, FIM2/3) separately and together. Summaries against BPZE1 whole cell extract will be provided based on results from IgG.

Listings will be provided for systemic immunogenicity data as collected based on the Immunogenicity Analysis Set.

For GMT, descriptive statistics will be provided for each acellular pertussis antigen as well as BPZE1 whole cell extract (the number of subjects with non-missing assessments, geometric means with 95% CI, geometric SD, median, minimum, maximum) For each antigen, if IgA and IgG results are reported as lower than the minimal limit of assay detection, a value equal to half of the minimal limit of assay detection will be imputed in the calculation. The minimal limit of assay detection for each of the following antibody titers PT, FHA, PRN, FIM 2, FIM3, and BPZE1 whole cell will be established following assay validation and prior to database lock.

GMT will be calculated as anti-logarithm of \sum (log-transformed titer/number of subjects with titer information). The 95% CI for GMT will be calculated as the anti-log transformation of upper and lower limits for a 2-sided CI of the mean of the log-transformed titers.

GMFR will be calculated as anti-logarithm of \sum [log-transformed titer ratio of Y_i/B_i]/number of subjects with titer information], where Y_i is the post-dose titer and B_i is the baseline titer for subject i . The same data summaries will be provided as GMT. For any antibody titer below the minimal limit of assay detection, the value to be imputed in the calculation will follow the same as GMT.

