2.5.2 Secondary Mucosal Immunogenicity Endpoints

The secondary mucosal immunogenicity S-IgA ELISA endpoints (nasal mucosal secretion sampling) of this study are:

- Proportion of subjects who achieve seroconversion against any pertussis-specific antigen (PT, PRN, FHA, FIM 2/3, or BPZE1 whole cell extract) over baseline:
 - At least 1 antigen **on each** of the Days 29, 78, 113, 169, or 254
 - At least 1 antigen **on any** of the Days 29, 78, 113, 169, or 254
 - At least **any** 1 antigen **on all** Days 29, 78, 113, 169, and 254.
- Proportion of subjects who achieve seroconversion against BPZE1 whole cell extract over baseline:
 - **On either** Day 29 (prime) or 113 (boost)
 - **On both** Days 29 (prime) and 113 (boost).
- Proportion of subjects who achieve seroconversion against aP antigens PT, FHA, and PRN over baseline:
 - **On either** Days 29 (prime) or 113 (boost)
 - **On both** Days 29 (prime) and 113 (boost).
- Proportion of subjects who achieve seroconversion for any 2 or more pertussis antigens (PT, PRN, FHA, or BPZE1 whole cell extract) over baseline:
 - **On each** of Days 29, 78, 113, 169, or 254

- On **any** of Days 29, 78, 113, 169 or 254
- At least the **same 2 antigens** on **all** Days 29, 78, 113, 169, and 254.
- Proportion of subjects who demonstrate boosting against each pertussis antigen (PT, FHA, PRN, FIM 2/3, and BPZE1 whole cell extract) on Day 113. Boost is defined as at least a 2-fold increase from pre-boost sample taken at Day 78.
- The GMFR against each pertussis antigen (PT, FHA, PRN, FIM 2/3, and BPZE1 whole cell extract):
 - On Days 29, 78, 113, 169, and 254 **over baseline** (Day 1)
 - On Days 113, 169, and 254 **over pre-boost** (Day 78)
 - The maximum **over baseline** on either Day 29 or 78 (post-priming response)
 - The maximum **over pre-boost** (Day 78) on any of the Days 113, 169, or 254 (post-boost response)
 - The maximum **during** the study.
- The GMT against each pertussis antigen (PT, FHA, PRN, FIM 2/3, and BPZE1 whole cell extract):
 - On Days 29, 78, 113, 169, and 254
 - The maximum on Days 29 or 78 (**after priming** dose)
 - The maximum after Days 113, 169, or 254 (**after boosting** dose)
 - The maximum **during** the study.

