3.2.2. Secondary Endpoints

3.2.2.1. Secondary Systemic Immunogenicity Endpoints

The secondary systemic immunogenicity (serum sampling [expressed separately for IgG, IgA, and IgG or IgA ELISA when possible]) endpoints of this study are:

- Proportion of subjects who achieve seroconversion against pertussis antigen (PT, FHA, PRN, FIM 2/3, or BPZE1 whole cell extract) over baseline for:
 - At least 1 antigen **on each** of the Days 29, 85, 113, 169, or 254
 - At least 1 antigen **on any** of the Days 29, 85, 113, 169, or 254
 - At least **any 1** antigen **on all** Days 29, 85, 113, 169, and 254
- Systemic seroconversion is defined as a 2-fold increase over the baseline value or a 4-fold increase over the minimal limit of assay detection (whenever the baseline value falls below the limits of assay detections). Both IgG and IgA ELISA will measure antibodies against the following pertussis-specific antigens of PT, FHA, PRN, and FIM 2/3, and IgG ELISA will measure antibodies against broader pertussis-specific antigens in BPZE1 whole cell extract.
- Serum baseline samples taken at Day 1 prior to vaccination.
- Proportion of subjects who achieve seroconversion (IgG ELISA only) against BPZE1 whole cell extract over baseline:
 - On **either** Day 29 (prime) or 113 (boost)
 - On **both** Days 29 (prime) and 113 (boost).
- Proportion of subjects who achieve seroconversion against the acellular pertussis antigens PT, FHA, and PRN over baseline:
 - On **either** Day 29 (prime) or 113 (boost)
 - On **both** Days 29 (prime) and 113 (boost).
- Proportion of subjects who achieve seroconversion against 2 or more pertussis antigens (PT, FHA, PRN, FIM 2/3, and BPZE1 whole cell extract) over baseline:
 - On **each** of the Days 29, 85, 113, 169, or 254
 - On **any** of the Days 29, 85, 113, 169, or 254

- At least the same **2 antigens** on **all** Days 29, 85, 113, 169, and 254.
- Proportion of subjects who demonstrate boosting for each pertussis antigen (PT, FHA, PRN, FIM 2/3, and BPZE1 whole cell extract) on Day 113. Boost is defined as at least a 2-fold increase from the pre-boost sample taken on Day 85.
- The Geometric Mean Fold rise (GMFR) against each pertussis antigen (PT, FHA, PRN, FIM 2/3, and BPZE1 whole cell extract):
 - On Days 29, 85, 113, 169, and 254 **over baseline** (Day 1)
 - On Days 113, 169, and 254 **over pre-boost** (Day 85)
 - The maximum **over baseline** on either Day 29 or 85 (post-priming response)

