4.6. Handling of Missing Data

Data will be presented in the listings as reported. For summaries and analysis, the following conventions apply.

Immunogenicity Data

No Imputation methods will be used for missing immunogenicity data and all analyses will be based on complete records only.

Any pertussis antigen specific antibody titer (PT, FHA, PRN, FIM 2/3, or BPZE1 whole cell extract) from either serum or nasal mucosal sample that is below the minimal limit of assay detection will be imputed with a value equal to half of the minimal limit of assay detection of the antigen specific antibody titer.

Adverse Event Data

Missing date will be imputed as described in [Appendix 13.4](#). Missing information regarding ‘relationship to study vaccine’ or ‘severity’ will be imputed as related to study vaccine and severe, as the worst-case scenario.

Prior/Concomitant Medication Data

Missing date will be imputed as described in [Appendix 13.4](#).

5. Subject Disposition

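### When the pre-boost value is below the detection limit, half-LOD imputation reduces the 2-fold boost rule to merely reaching the LOD on Day 113

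*SAP*

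**What the plan says.** **Boost rule.** SAP 8.2.1.5 reads: "Boost is defined as at least a 2-fold increase from the pre-boost baseline". The endpoint lists use the same bare ratio. For serum, SAP 3.2.2.1 has "Boost is defined as at least a 2-fold increase from the pre-boost sample taken on Day 85". For nasal secretions, Protocol 2.5.2 has "Boost is defined as at least a 2-fold increase from pre-boost sample taken at Day 78". Protocol 2.5.1 and 7.2 and SAP 3.2.2.2 repeat it. None of these places says what happens when the pre-boost value is undetectable. SAP 8.2.2 applies the systemic analyses to mucosal endpoints with two exceptions (which sample is the pre-boost value, and the two reporting scales). Neither exception adds a detection-limit condition.

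**Imputation.** SAP 4.6 opens with "For summaries and analysis, the following conventions apply" and then states that a serum or nasal titer below the detection limit "will be imputed with a value equal to half of the minimal limit of assay detection of the antigen specific antibody titer". The substitution therefore enters the boost ratio.

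**Seroconversion, for comparison.** The mucosal rule in SAP 8.1 has a separate branch for undetectable baselines: "a 4-fold increase over the minimal limit of assay detection (whenever the baseline value falls below the limits of assay detection". SAP 8.2.1 has the same branch for serum.

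**The concern.** The boost rule is meant to identify subjects whose titer at least doubled. Below the LOD the pre-boost titer is unknown, and the analysis uses a constant instead. Half the LOD is a reasonable filler for a geometric mean, but as the denominator of a 2-fold responder rule it puts the threshold exactly at the LOD. Going from not detected to just detected is then a response, whatever the actual change was.

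What is at stake is the reported boost proportion per antigen, in serum and on both nasal scales. Protocol 3.1.1 describes showing boosting as critical. The endpoint is secondary and descriptive and the study tests no formal hypothesis, so no error rate or sample size is affected.

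**Working it through.** The documents state no figure for the boost endpoint, so there is none to reproduce first.

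**Inputs from the documents:** boost if Day 113 / pre-boost is at least 2 (SAP 8.2.1.5); values below LOD set to 0.5 x LOD (SAP 4.6); seroconversion from an undetectable baseline needs 4 x LOD (SAP 8.1, 8.2.1). The LOD values are not given, but the result in LOD units does not depend on them.

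**1. Threshold.** Pre-boost below LOD gives a denominator of 0.5, so boost requires Day 113 of at least 2 x 0.5 = 1.0 x LOD.

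| Pre-boost | Day 113 (x LOD) | Scored fold | Boost? | Reaches 4 x LOD? |
|---|---|---|---|---|
| below LOD | 0.99 | 0.5/0.5 = 1.0 | no | no |
| below LOD | 1.00 | 1.0/0.5 = 2.0 | yes | no |
| below LOD | 1.50 | 1.5/0.5 = 3.0 | yes | no |
| below LOD | 3.99 | 3.99/0.5 = 7.98 | yes | no |
| 1.0 x LOD | 1.00 | 1.0 | no | no |

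A measured 1.00/0.99 = 1.01-fold change is scored as 2-fold. The last row shows that the problem disappears once the pre-boost value is detectable.

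**2. Standardized nasal scale.** If total IgA on Day 113 is r times its pre-boost value, the scored fold on reaching the LOD is 2/r. That is 2.5 when r = 0.8 and 1.6 when r = 1.25, so reaching the LOD may or may not count.

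**3. False boosts with no true change.** These assumptions are not in the documents: true level c x LOD at both visits, independent normal error on log2 titer, SD s = 0.5. With x and y the pre-boost and Day 113 log2 values in LOD units,

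P(boost) = P(x < 0) P(y >= 0) + P(x >= 0, y - x >= 1).

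- c = 0.5: 0.977 x 0.023 + 0.000 = 2%
- c = 0.7: 0.848 x 0.152 + 0.000 = 13%
- c = 0.85: 0.680 x 0.320 + 0.001 = 22%
- c = 1.0: 0.500 x 0.500 + 0.003 = 25%
- Clearly detectable subject: 1 - Phi(1/(0.5 x 1.414)) = 1 - Phi(1.414) = 8%

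Over s = 0.3 to 0.7 the rule as written gives 0-26% for c from 0.5 to 1.0. The background for detectable subjects goes from 1 - Phi(2.357) = 0.9% to 1 - Phi(1.010) = 15.6%. The relative excess is therefore largest when the assay is precise.

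**4. Candidate guards, s = 0.5.** With a guard at 2 x LOD, the first term becomes P(x < 0) P(y >= 1). At c = 1.0 this is 0.500 x 0.0228 + 0.003 = 0.0145, and it is lower at smaller c. With a guard at 4 x LOD the rate is at most about 0.3%. For a true 4-fold rise (mean of y raised by 2), the proportion scored as boosted is:

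| True pre-boost level | As written | 2 x LOD guard | 4 x LOD guard |
|---|---|---|---|
| 0.5 x LOD | 96% | 50% | 3% |
| 0.7 x LOD | 95% | 81% | 23% |
| 0.85 x LOD | 93% | 89% | 47% |

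Worked entry, 0.7 x LOD with the 2 x LOD guard: P(x < 0) = 0.848 and P(y >= 1) = Phi(0.971) = 0.834. The product is 0.707; adding 0.101 from pre-boost readings at or above LOD gives 0.81. A clearly detectable subject with the same rise is scored as boosted 92% of the time.

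**The case against.** The best defence is that a 2-fold rule always misclassifies some noise. At log2 SD 0.5 it does so for about 8% of clearly detectable subjects, and at a true level of 0.5 x LOD the rule as written does better than that (2%). This stands: the excess is confined to true levels near the LOD and should be judged against 8%, not against zero.

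A second defence is that boost and seroconversion are different endpoints and need not share a guard. This also stands in part. A reader might infer that boost should simply adopt 4 x LOD. The last table shows the cost: for a true 4-fold rise, detection falls to 3-47%, so that guard would remove most genuine boosts from undetectable levels.

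Third, Protocol 7.7.3 ties a detection-limited mucosal response rate to Day 78 as well as screening, and fold rises over pre-boost and subject listings are planned. These help a careful reader, but they carry other names, the Day 78 rate covers nasal samples only, and none of them changes how boost is scored.

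A reader might also infer that false boosts gather in the Boostrix-primed arms C and D and distort A versus C and C versus D. The documents do not support this. For nasal S-IgA it rests on the plan's hypothesis of weaker mucosal immunity after Boostrix, and values far below the LOD produce few false boosts. For serum, Protocol 3.1.1 expects a smaller response to the acellular antigens after BPZE1, which could put more undetectable values in A and B. C and D are both Boostrix-primed and randomized, so if the BPZE1 boost has no effect, false boosts are equal in expectation and that contrast is not biased.

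**Conclusion.** The point holds for subjects whose pre-boost value is below LOD, and only for them. For these subjects the boost rule is the same as reaching 1 x LOD on Day 113, exactly for serum and absolute nasal titers and approximately on the total-IgA-standardized scale. It would be wrong to read it as making every Day 113 value at the LOD a boost: with a detectable pre-boost value the ratio there is at most 1.

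The size is conditional. With independent lognormal error at log2 SD 0.5 and no true change, false boosts are 13-25% at 0.7-1.0 x LOD, against about 8% for detectable subjects and 2% at 0.5 x LOD. The proportion below LOD and its split by arm are not in the documents, so neither the trial-level effect nor its direction between arms can be stated. This is a modest but real classification fault in a secondary descriptive endpoint, and it is worth correcting before the data are seen.

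**What to change.** In SAP 8.2.1.5 and 8.2.2, and in the matching endpoint text (SAP 3.2.2.1 and 3.2.2.2; Protocol synopsis, 2.5.1, 2.5.2 and 7.2), add that when the pre-boost value is below LOD, boost requires a Day 113 value of at least 2 x LOD. This is the smallest value that demonstrates a 2-fold rise from an unknown value under the LOD. It is equivalent to entering the LOD, rather than half of it, as the denominator for this endpoint, and in that form it carries over to the standardized nasal scale.

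Report the number of subjects below LOD pre-boost by arm and antigen, and tabulate boost under the plan's own 4 x LOD convention as a sensitivity analysis.

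The editing cost is one sentence plus one table row per antigen. SAP 8.2.1 sets the LODs after assay validation and before database lock, so the rule can be fixed now in LOD units. The statistical cost is lost sensitivity: for a true 4-fold rise from 0.5-0.85 x LOD, about 50-89% are scored as boosted at 2 x LOD, against 93-96% as written. Boost proportions will be lower where many pre-boost values are undetectable, which is why the counts below LOD should be shown beside them.
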